**Treatment Modification for MLN0128 (TAK-228)-Related Adverse Events**

Event	CTCAE. V4 Grade	Action to be Taken
AST or ALT	Grade 1 or Grade 2 (without total bilirubin elevation > grade 1)	Maintain dose level of MLN0128 (TAK-228)
	Grade 3 (without total bilirubin elevation > grade 1)	Omit dose of MLN0128 (TAK-228) until resolved to ≤ Grade 1 or baseline, then: 
 
• If resolved in ≤ 7 days, maintain dose level of MLN0128 (TAK-228)
 
• If resolved in > 7 days, resume treatment at ↓ 1 dose level of MLN0128 (TAK-228)
 
• If not resolved in 21 days, then discontinue patient from study treatment.
 
• Permanently discontinue study treatment if in combination with Grade 2 total bilirubin elevation when alternative causes cannot be identified (ie, Hy’s Law);
 

	Grade 4	Permanently discontinue study treatment if in combination with Grade 2 total bilirubin elevation when alternative causes cannot be identified (ie, Hy’s Law).
RENAL		
Creatinine	Grade 1	Maintain dose level of MLN0128 (TAK-228)
	Grade 2	Omit dose of MLN0128 (TAK-228) until resolved to ≤ Grade 1 or baseline, then resume treatment at the same dose level. Patients will be instructed to increase their fluid intake until resolution to ≤ Grade 1 or baseline.
	Grade 3	Omit dose of MLN0128 (TAK-228) until resolved to ≤ Grade 1 or baseline then: 
 
• If resolved in ≤ 7 days, maintain dose level of MLN0128 (TAK-228)
 
• If resolved in > 7 days, resume treatment at ↓ 1 dose level of MLN0128 (TAK-228)
 
• If not resolved in 21 days, then discontinue patient from study treatment.
 

RESPIRATORY		
	Grade 1	Maintain dose level of MLN0128 (TAK-228)

Non-infectious Pneumonitis	Grade 2	Omit dose of MLN0128 (TAK-228) until resolved to Grade $\leq 1$ , then: 
 
• Restart at <math>\downarrow 1</math> dose level of MLN0128 (TAK-228)
 
• Discontinue MLN0128 (TAK-228) if failure to recover within 4 weeks
 

	Grade 3	Omit dose of MLN0128 (TAK-228) until resolved to Grade $\leq 1$ , then: 
 
• Consider re-initiating MLN0128 (TAK-228) at <math>\downarrow 1</math> dose level of MLN0128 (TAK-228)
 
• If toxicity recurs at Grade 3, discontinue MLN0128 (TAK-228)
 

Treatment Modification for MLN0128 (TAK-228)-Related Adverse Events		
Event	CTCAE. V4 Grade	Action to be Taken
	Grade 4	Permanently discontinue patient from the study treatment
SKIN AND SUBCUTANEOUS TISSUE DISORDERS		
Rash (maculo-papular)	Grade 1	Maintain dose level of MLN0128 (TAK-228). Consider initiation appropriate skin toxicity therapy (such as antihistamines, topical corticosteroids)
	Grade 2	Maintain dose level of MLN0128 (TAK-228). Initiate/intensify appropriate skin toxicity therapy (such as antihistamines, topical corticosteroids)
	Grade 3	Omit dose of MLN0128 (TAK-228) until resolved to Grade $\leq 1$ , then: 
 
• If resolved in <math>\leq 7</math> days, maintain at same dose of MLN 0218
 
• If resolved in <math>> 7</math> days, resume at <math>\downarrow 1</math> dose level of MLN0128 (TAK-228)
 
• If not resolved in 21 days, then discontinue patient from study treatment.
 

	Grade 4	Patients who develop Grade 4 rash should permanently discontinue study treatment, unless they derive clinical benefit, in which case they may be retreated at a reduced dose level after recover to $\leq$ Grade 1 severity. Grade 4 rash is defined as rash acneiform/papulopustular with papules and/or pustules covering any % body surface area, which may or may not be associated with symptoms of pruritus or tenderness, and are associated with extensive superinfection with intravenous (IV) antibiotics indicated; life threatening consequences (NCI CTCAE Version 4.03, effective date 14 June 2010).
INVESTIGATIONS		
Cholesterol high and/or hypertriglyceridemia	Grade 1	Maintain MLN0128 (TAK-228) dose level
	Grade 2	Maintain dose if tolerable, if toxicity becomes intolerable, omit dose MLN0128 (TAK-228) until resolved to $\leq 1$ , then restart MLN0128 (TAK-228) as the same dose level
	Grade 3	Omit dose of MLN0128 (TAK-228) until resolved to Grade $\leq 1$ , then restart at $\downarrow 1$ dose level of MLN0128 (TAK-228)
	Grade 4	Permanently discontinue patient from the study treatment

OTHER ADVERSE EVENTS		
Other AEs	Grade 1-2	Maintain MLN0128 (TAK-228)
	Grade 3	Omit dose of MLN0128 (TAK-228) until resolved to $\leq$ Grade 1, then: 
 
• If resolved in <math>\leq</math> 7 days, maintain at same dose of MLN 0218
 
• If resolved in <math>></math> 7 days, resume at <math>\downarrow</math>1 dose level of MLN0128 (TAK-228)
 
• If not resolved in 21 days, then discontinue patient from study treatment.
 

	Grade 4	Permanently discontinue patient from the study treatment
		Note: Omit dose for $\geq$ Grade 3 vomiting or Grade 3 nausea only if the vomiting or nausea

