### **5.3 Duration of Therapy**

In the absence of treatment delays due to adverse event(s), treatment may continue until one of the following criteria applies:

- Disease progression (at the discretion of the PI, patients who continue to derive clinical benefit

may be treated beyond progression; see [Section 5.3.1](#) for details),

- Intercurrent illness that prevents further administration of treatment,
- Unacceptable adverse event(s),
- Patient decides to withdraw from the study, or
- General or specific changes in the patient's condition render the patient unacceptable for further treatment in the judgment of the investigator.

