## 6. DOSING DELAYS/DOSE MODIFICATIONS

Toxicities will be graded using the NCI CTCAE Version 4.0 and dose modifications of the study drugs will be made for hematologic and other toxicities. Patients experiencing study drug related toxicities that require a delay in dosing for >21 days will be discontinued from further participation in this study. In the event that patients must have treatment delayed with a treatment cycle due to toxicities, those doses held during a cycle will not be made up.

Dose Level	MLN0128 (TAK-228) Dose
0	3 mg flat dose daily continuous
-1	2 mg flat dose daily continuous
-2	2 mg daily 5 days/ week
-3	1 mg 5 days/week
-4	Withdraw from study

Treatment Modification for MLN0128 (TAK-228)-Related Adverse Events		
Event	CTCAE. V4 Grade	Action to be Taken
QTc prolongation	≥ Grade 3 or > 60ms change from baseline on at least two separate ECGs	
First Occurrence:
 
 
• Omit MLN0128 (TAK-228) dose
 
• Perform an analysis of potassium and magnesium, and if below lower limit of normal, correct with supplements to within normal limits. Concomitant medication usage must be reviewed.
 
• Perform a repeat ECG within one hour of the first QTcF of 500 ms
 
• If QTcF remains > 500 ms, repeat ECG as clinically indicated, but at least once a day until the QTcF returns to < 480 ms. Seek cardiologist input
 
• Once QTcF prolongation has resolved, MLN0128 (TAK-228) may be restarted at a one lower dose level
 
 
Second Occurrence:
 
 
• Permanently discontinue patient from the study treatment
 

	Other Cardiac Events	Grade 1-2
	Grade 3	
Omit dose of MLN0128 (TAK-228) until resolved to ≤ Grade 1
 
 
• If resolved within 7 days, then resume at same dose level of MLN0128 (TAK-228).
 
• If resolved in >7 days, resume at ↓1 dose level of MLN0128 (TAK-228).
 
• If not resolved in 21 days, then discontinue patient from study treatment.
 

	Grade 4	Permanently discontinue patient from the study treatment
Treatment Modification for MLN0128 (TAK-228)-Related Adverse Events		
Event	CTCAE. V4 Grade	Action to be Taken
ENDOCRINE		

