	Grade 2	Maintain MLN0128 (TAK-228) dose level if tolerable, if toxicity becomes intolerable omit dose of MLN0128 (TAK-228) until resolved to Grade $\leq$ 1, then restart at the same dose level
	Grade 3	Omit dose of MLN0128 (TAK-228) until resolved to Grade $\leq$ 1, then restart at $\downarrow$ 1 dose level of MLN0128 (TAK-228), If not resolved in 21 days, then discontinue patient from study treatment.
	Grade 4	Permanently discontinue patient from the study treatment
GENERAL DISORDERS		
Fatigue (asthenia)	Grade 1-2	Maintain MLN0128 (TAK-228) dose level
	Grade 3	Omit dose of MLN0128 (TAK-228) until resolved to $\leq$ Grade 1, then: 
 
• If resolved in <math>\leq</math> 7 days, maintain dose level of MLN0128 (TAK-228)
 
• If resolved in <math>></math> 7 days, <math>\downarrow</math> 1 dose level of MLN0128 (TAK-228)
 
• If not resolved in 21 days, then discontinue patient from study treatment.
 

	Grade 4	Patients who develop Grade 4 nonhematological toxicities (with the exception of isolated non-clinically significant laboratory values) should permanently discontinue study treatment, unless they derive clinical benefit, in which case they may be retreated at a reduced dose level after recovery to $\leq$ Grade 1 severity.
HEMATOLOGIC		
Neutropenia (ANC)	Grade 1-2	Maintain dose level of MLN0128 (TAK-228)

Grade 3	Omit dose of MLN0128 (TAK-228) until resolved to $\leq$ Grade 1 or baseline, then: 

• If resolved in <math>\leq 7</math> days, maintain dose level of MLN0128 (TAK-228)

• If resolved in <math>> 7</math> days, resume treatment at <math>\downarrow 1</math> dose level of MLN0128 (TAK-228)

• If not resolved in 21 days, then discontinue

---------	--

Treatment Modification for MLN0128 (TAK-228)-Related Adverse Events		
Event	CTCAE. V4 Grade	Action to be Taken
		patient from study treatment.
	Grade 4	Permanently discontinue patient from the study treatment
Febrile Neutropenia	Grade 3	Omit dose of MLN0128 (TAK-228) until resolved to Grade 1 or baseline, then: 
 
• If resolved in <math>\leq 7</math> days, resume treatment at <math>\downarrow 1</math> dose level of MLN0128 (TAK-228)
 
• If resolved in <math>> 7</math> days, discontinue MLN0128 (TAK-228)
 

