Thrombocytopenia	Grade 1-2	Maintain dose level of MLN0128 (TAK-228)
	Grade 3	Omit dose of MLN0128 (TAK-228) until resolved to $\leq$ Grade 1 or baseline then: 
 
• If resolved in <math>\leq 7</math> days, resume treatment at <math>\downarrow 1</math> dose level of MLN0128 (TAK-228)
 
• If resolved in <math>> 7</math> days, discontinue MLN0128 (TAK-228)
 

	Grade 4	Permanently discontinue patient from the study treatment
HEPATIC		
Bilirubin	Grade 1	Maintain dose level of MLN0128 (TAK-228)
	Grade 2 (with ALT or AST grade 1 or 2)	Omit dose of MLN0128 (TAK-228) until resolved to $\leq$ Grade 1 or baseline, then resume at the same dose level of MLN0128 (TAK-228)
	Grade 3 (with ALT or AST grade 1 or 2)	Omit dose of MLN0128 (TAK-228) until resolved to $\leq$ Grade 1 or baseline, then: 
 
• If resolved in <math>\leq 7</math> days, maintain same dose level of MLN0128 (TAK-228)
 
• If resolved in <math>> 7</math> days but less than 21 days, resume treatment at <math>\downarrow 1</math> dose level of MLN0128 (TAK-228).
 
• If not resolved in 21 days, then discontinue patient from study treatment.
 

	Grade 4	Permanently discontinue patient from the study treatment

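### The AST/ALT rows order less for an isolated Grade 4 rise than for Grade 3, the general Grade 4 rule is not linked to them, and the Grade 3 Hy's Law stop contradicts its row heading

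*Combined protocol and SAP*

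**What the plan says.** All of this is in the Section 6 table of treatment modifications for drug-related adverse events, unless another section is named.

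- **AST or ALT, Grade 3.** The row is headed "Grade 3 (without total bilirubin elevation > grade 1". It orders a hold until recovery, then the same dose or one level lower depending on whether recovery took more than 7 days. It adds: "If not resolved in 21 days, then discontinue patient from study treatment". Its last bullet is the Hy's Law stop: "Permanently discontinue study treatment if in combination with Grade 2 total bilirubin elevation when alternative causes cannot be identified".
- **AST or ALT, Grade 4.** The cell repeats the Hy's Law stop and contains nothing else. Its heading sets no bilirubin limit.
- **Bilirubin.** The Grade 3 row is headed "Grade 3 (with ALT or AST grade 1 or 2", and the Grade 2 row carries the same limit. Grade 4 bilirubin is a permanent stop without such a limit.
- **Fatigue, Grade 4.** This cell holds a sentence of general scope: "Patients who develop Grade 4 nonhematological toxicities (with the exception of isolated non-clinically significant laboratory values) should permanently discontinue study treatment". An exception lets a patient who is benefiting restart at a lower dose once the event has settled to Grade 1 or below.
- **Other AEs.** Grade 3 is held, with a 21-day limit; Grade 4 is a permanent stop.
- **Section 6, opening text.** A 21-day limit applies to "Patients experiencing study drug related toxicities that require a delay in dosing for" longer than that.
- **Section 5.3.** Treatment may also end when changes in the patient's condition "render the patient unacceptable for further treatment in the judgment of the investigator".

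**The concern.** A dose-modification table should not ask for less as toxicity worsens. In the AST/ALT rows, an isolated Grade 3 rise brings a mandatory hold and a time limit. An isolated Grade 4 rise, with bilirubin no higher than Grade 1, brings no order at all. A physician who uses only the liver rows has no instruction for the worse event.

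The Hy's Law bullet raises a second problem. It applies to patients with Grade 2 bilirubin, but its row is limited to patients whose bilirubin is not above Grade 1. The hold in that row falls under the same limit. A patient with Grade 3 AST/ALT and Grade 2 or 3 bilirubin therefore has no ordered hold in the hepatic rows while other causes are investigated, which is when a hold matters most.

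At stake is continued dosing during possible drug-induced liver injury. Response rate, progression-free survival and the two-stage design are untouched.

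**Working it through.** No formula in the plan applies, so the check is a mapping. Take AST/ALT Grade 3 or 4 against bilirubin Grade 0 to 4, giving 2 x 5 = 10 combinations, and find the hepatic row that orders a hold or a stop for each. Two reading choices favour the plan: the Hy's Law bullet is applied despite its row heading, and its Grade 2 is taken to mean Grade 2 or higher.

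| AST/ALT | Bilirubin 0-1 (2 combinations) | Bilirubin 2-3 (2 combinations) | Bilirubin 4 (1 combination) |
|---|---|---|---|
| Grade 3 | Hold, 21-day limit | Stop if no alternative cause; nothing while the cause is open | Stop (bilirubin row) |
| Grade 4 | Nothing | Stop if no alternative cause; nothing while the cause is open | Stop (bilirubin row) |

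**Hepatic rows alone**
- No alternative cause: 2 of 10 without an order (AST/ALT Grade 4 with bilirubin 0 or 1).
- Cause still open: 2 (Grade 3 with bilirubin 2-3) + 2 (Grade 4 with bilirubin 0-1) + 2 (Grade 4 with bilirubin 2-3) = 6 of 10.

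**Adding the general Grade 4 rule from the Fatigue row**
- Rise judged clinically significant: 2 - 2 = 0 with no alternative cause, and 6 - 4 = 2 with the cause open. The remaining two are AST/ALT Grade 3 with bilirubin 2 or 3. The general rule cannot reach them because neither value is Grade 4.
- Isolated rise judged exempt as a laboratory value: the two Grade 4 combinations with bilirubin 0-1 return, giving 2 and 2 + 2 = 4.

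**Strictly literal reading (bilirubin exactly Grade 2), no alternative cause**
- Hepatic rows alone: 4 without an order, because bilirubin Grade 3 then matches no row.
- With the general rule: 1 (AST/ALT Grade 3 with bilirubin Grade 3).

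**Remaining backstops**
- The 21-day rule in the opening of Section 6 limits a delay that something else has required. The Grade 4 AST/ALT cell requires none.
- The Section 5.3 grounds rest on judgment and set no AST/ALT threshold.
- The Other AEs rows would supply a hold for the two Grade 3 combinations, 2 - 2 = 0, if they may be used for an event that has its own rows.

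The note that closes the table is incomplete in the text available, so nothing here rests on it.

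**The case against.** The strongest reply is that the protocol already deals with Grade 4. A transaminase rise is not hematological, so the general sentence tells the physician to stop, and the laboratory-value exemption is a discretion granted openly. This largely stands. A reader might infer from the AST/ALT cell that the protocol allows dosing to continue through any Grade 4 rise. The documents do not support that, because a clinically significant rise is probably covered. What remains is that the rule sits under another event, the liver rows do not point to it, and an isolated transaminase value is where its exemption is likely to be argued.

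Second, the Other AEs rows can be read as catching patients whom the hepatic headings exclude. That is arguable. But AST/ALT is a named event with its own rows, and a physician is not clearly directed to the residual category.

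Third, the Hy's Law bullet is evidently meant as an exception to its row, and it is repeated in the Grade 4 cell without conflict. So the documents do not support inferring that Hy's Law patients at Grade 3 are meant to continue. The intended stop is clear; the missing part is the hold before a cause is settled.

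Fourth, the drug is not an established cause. Section 7.1.1 lists ALT, AST and bilirubin increases among events with insufficient evidence of causation, and the Section 6 table covers drug-related events only. This limits how often the gap will matter.

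Finally, a reader might count the daily doses between scheduled chemistry tests as the exposure at risk. Section 10 allows 7 days either side of a visit and describes its calendar as an example to be modified, and an investigator can re-test or hold at any time. No dose bound follows.

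**Conclusion.** The point holds as a fault in the wording of a safety rule that should be corrected. Followed as written, the AST/ALT rows order less at Grade 4 than at Grade 3, and the Grade 3 row contradicts its own heading.

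The firmest gap is AST/ALT Grade 3 with bilirubin Grade 2 or 3 while causes are assessed: two of the ten combinations, which the general Grade 4 rule cannot reach. The isolated Grade 4 gap, another two combinations, is real within the AST/ALT rows but probably closed elsewhere when the rise is judged clinically significant.

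These counts assume that Grade 2 bilirubin means Grade 2 or higher and that Other AEs does not override a named event. They count situations, not patients. The documents give no Grade 4 AST/ALT rate, so no probability is claimed, and the event is probably uncommon. No efficacy figure or operating characteristic changes.

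**What to change.** Two wording changes to the Section 6 table:

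- **(a) AST or ALT, Grade 4.** Order an immediate hold for any Grade 4 rise. Then apply the general Grade 4 rule alone, written out in this cell: permanent discontinuation, with retreatment at a reduced dose only for clinical benefit and only after recovery to Grade 1 or below. Do not add a Grade 3-style resumption path, which would conflict with that rule.
- **(b) Hy's Law.** Remove the bullet from the Grade 3 row and create a row for AST or ALT Grade 3 or higher with total bilirubin Grade 2 or higher. Hold while causes are assessed, and discontinue permanently if no alternative cause is found. Otherwise follow the Grade 3 resumption and 21-day rules. AST/ALT Grade 4 follows (a), and bilirubin Grade 4 stays a permanent stop.

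With both changes, all ten combinations carry an ordered hold or stop, including while causes are open.

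The cost is an amendment to the table. No tests are added, because AST, ALT and bilirubin are already in the Section 10 chemistry panel. The downside is clinical: a patient with a brief isolated Grade 4 rise may miss doses or be discontinued, where the laboratory-value exemption might now spare them. Under Section 5.5 a patient removed for a reason other than progression is replaced, so a few extra replacements are possible. The change can still help the extension patients (10 each in cohorts 1 and 2, so 20, Section 13.2) and anyone still on treatment.

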## 7. ADVERSE EVENTS: LIST AND REPORTING REQUIREMENTS

Adverse event (AE) monitoring and reporting is a routine part of every clinical trial. The following list of AEs (Section 7.1) and the characteristics of an observed AE (Section 7.2) will determine whether the event requires expedited reporting via the CTEP Adverse Event Reporting System (CTEP-AERS) **in addition** to routine reporting.

### 7.1 Comprehensive Adverse Events and Potential Risks List (CAEPR) For MLN0128 (TAK-228, NSC 768435)

The Comprehensive Adverse Events and Potential Risks list (CAEPR) provides a single list of reported and/or potential adverse events (AE) associated with an agent using a uniform presentation of events by body system. In addition to the comprehensive list, a subset, the Specific Protocol Exceptions to Expedited Reporting (SPEER), appears in a separate column and is identified with bold and italicized text. This subset of AEs (SPEER) is a list of events that are protocol specific exceptions to expedited reporting to NCI (except as noted below). Refer to the 'CTEP, NCI Guidelines: Adverse Event Reporting Requirements' [http://ctep.cancer.gov/protocolDevelopment/electronic\\_applications/docs/aeguidelines.pdf](http://ctep.cancer.gov/protocolDevelopment/electronic_applications/docs/aeguidelines.pdf) for further clarification. *Frequency is provided based on 390 patients.* Below is the CAEPR for MLN0128 (TAK-228).

**NOTE:** Report AEs on the SPEER **ONLY IF** they exceed the grade noted in parentheses next to the AE in the SPEER. If this CAEPR is part of a combination protocol using multiple investigational agents and has an AE listed on different SPEERs, use the lower of the grades to determine if expedited reporting is required.

## 7.1.1 CAEPR for MLN0128 (TAK-228)

Version 2.3, July 28, 2019

Adverse Events with Possible Relationship to MLN0128 (TAK-228) (CTCAE 5.0 Term) [n= 390]			Specific Protocol Exceptions to Expedited Reporting (SPEER)
Likely (>20%)	Less Likely (<=20%)	Rare but Serious (<3%)	
BLOOD AND LYMPHATIC SYSTEM DISORDERS			
	Anemia		Anemia (Gr 2)
CARDIAC DISORDERS			
		Cardiac arrest	
		Ventricular fibrillation	
GASTROINTESTINAL DISORDERS			
	Abdominal pain		Abdominal pain (Gr 2)
Constipation			Constipation (Gr 2)
Diarrhea			Diarrhea (Gr 2)
	Dry mouth		Dry mouth (Gr 2)
	Dyspepsia		
Mucositis oral			Mucositis oral (Gr 2)
Nausea			Nausea (Gr 3)
Vomiting			Vomiting (Gr 3)
GENERAL DISORDERS AND ADMINISTRATION SITE CONDITIONS			
	Edema limbs		
Fatigue			Fatigue (Gr 3)
	Fever		Fever (Gr 2)
	General disorders and administration site conditions - Other (mucosal inflammation)		General disorders and administration site conditions - Other (mucosal inflammation) (Gr 2)
INFECTIONS AND INFESTATIONS			
	Urinary tract infection		Urinary tract infection (Gr 2)
INVESTIGATIONS			
	Creatinine increased		Creatinine increased (Gr 2)
		Electrocardiogram QT corrected interval prolonged	
	Platelet count decreased		Platelet count decreased (Gr 2)
	Weight loss		Weight loss (Gr 2)
METABOLISM AND NUTRITION DISORDERS			
Anorexia			Anorexia (Gr 2)
	Dehydration		Dehydration (Gr 2)
Hyperglycemia			Hyperglycemia (Gr 3)
	Hypokalemia		Hypokalemia (Gr 2)
	Hypomagnesemia		Hypomagnesemia (Gr 2)
	Hypophosphatemia		Hypophosphatemia (Gr 2)
MUSCULOSKELETAL AND CONNECTIVE TISSUE DISORDERS			
	Arthralgia		
	Back pain		Back pain (Gr 2)

Adverse Events with Possible Relationship to MLN0128 (TAK-228) (CTCAE 5.0 Term) [n= 390]			Specific Protocol Exceptions to Expedited Reporting (SPEER)
Likely (>20%)	Less Likely (<=20%)	Rare but Serious (<3%)	
	Pain in extremity		
NERVOUS SYSTEM DISORDERS			
	Dizziness		Dizziness (Gr 2)
	Dysgeusia		Dysgeusia (Gr 2)
	Headache		Headache (Gr 2)
PSYCHIATRIC DISORDERS			
	Insomnia		
RENAL AND URINARY DISORDERS			
	Acute kidney injury		
RESPIRATORY, THORACIC AND MEDIASTINAL DISORDERS			
	Cough		Cough (Gr 2)
	Dyspnea		Dyspnea (Gr 2)
	Oropharyngeal pain		
		Pneumonitis	
SKIN AND SUBCUTANEOUS TISSUE DISORDERS			
	Pruritus		Pruritus (Gr 2)
	Rash maculo-papular		Rash maculo-papular (Gr 2)

This table will be updated as the toxicity profile of the agent is revised. Updates will be distributed to all Principal Investigators at the time of revision. The current version can be obtained by contacting [[contact]](mailto:[contact]). Your name, the name of the investigator, the protocol and the agent should be included in the e-mail.

**Adverse events reported on MLN0128 (TAK-228) trials, but for which there is insufficient evidence to suggest that there was a reasonable possibility that MLN0128 (TAK-228) caused the adverse event:**

**BLOOD AND LYMPHATIC SYSTEM DISORDERS** - Blood and lymphatic system disorders - Other (hyperviscosity syndrome); Blood and lymphatic system disorders - Other (Raynaud's phenomenon); Febrile neutropenia

**CARDIAC DISORDERS** - Heart failure; Pericardial effusion; Sinus tachycardia; Ventricular arrhythmia

**EYE DISORDERS** - Blurred vision; Eye pain; Photophobia; Vision decreased

**GASTROINTESTINAL DISORDERS** - Abdominal distension; Colitis; Dysphagia; Esophagitis; Gastritis; Gastroesophageal reflux disease; Gastrointestinal disorders - Other (intestinal obstruction); Gastrointestinal disorders - Other (intestinal perforation); Gastrointestinal disorders - Other (salivary hypersecretion); Hemorrhoids; Ileus; Oral pain; Pancreatitis; Small intestinal obstruction; Small intestinal perforation; Toothache

**GENERAL DISORDERS AND ADMINISTRATION SITE CONDITIONS** - Chills; Flu like symptoms; Gait disturbance; General disorders and administration site conditions - Other (groin pain); Malaise; Non-cardiac chest pain; Pain

**HEPATOBIILIARY DISORDERS** - Gallbladder obstruction

**IMMUNE SYSTEM DISORDERS** - Allergic reaction

**INFECTIONS AND INFESTATIONS** - Abdominal infection; Infections and infestations - Other (cystitis); Infections and infestations - Other (lower respiratory tract infection); Infections and infestations - Other (mucosal infection); Infections and infestations - Other (parotid gland); Kidney infection; Lung infection; Papulopustular rash; Sepsis; Skin infection; Upper respiratory infection

**INJURY, POISONING AND PROCEDURAL COMPLICATIONS** - Fall; Fracture; Injury, poisoning and

procedural complications - Other (accidental overdose); Injury, poisoning and procedural complications - Other (postoperative fever); Injury, poisoning and procedural complications - Other (subdural hemorrhage); Tracheal obstruction

**INVESTIGATIONS** - Alanine aminotransferase increased; Alkaline phosphatase increased; Aspartate aminotransferase increased; Blood bilirubin increased; Blood lactate dehydrogenase increased; Cholesterol high; GGT increased; Lipase increased; Lymphocyte count decreased; Neutrophil count decreased; White blood cell decreased

**METABOLISM AND NUTRITION DISORDERS** - Acidosis; Hypercalcemia; Hyperkalemia; Hyponatremia; Hypertriglyceridemia; Hyperuricemia; Hypoalbuminemia; Hypocalcemia; Hyponatremia; Metabolism and nutrition disorders - Other (severe chronic malnutrition); Metabolism and nutrition disorders - Other (vitamin D deficiency)

**MUSCULOSKELETAL AND CONNECTIVE TISSUE DISORDERS** - Bone pain; Chest wall pain; Flank pain; Generalized muscle weakness; Muscle cramp; Myalgia

**NEOPLASMS BENIGN, MALIGNANT AND UNSPECIFIED (INCL CYSTS AND POLYPS)** - Neoplasms benign, malignant and unspecified (incl cysts and polyps) - Other (non-hodgkin lymphoma); Treatment related secondary malignancy

**NERVOUS SYSTEM DISORDERS** - Ataxia; Intracranial hemorrhage; Lethargy; Nervous system disorders - Other (carotid artery occlusion); Nervous system disorders - Other (neuropathy peripheral); Paresthesia; Radiculitis; Stroke; Tremor

**PSYCHIATRIC DISORDERS** - Anxiety; Confusion; Depression; Psychiatric disorders - Other (mental status changes)

**RENAL AND URINARY DISORDERS** - Dysuria; Hematuria; Proteinuria; Renal and urinary disorders - Other (strangury)

**REPRODUCTIVE SYSTEM AND BREAST DISORDERS** - Vaginal hemorrhage

**RESPIRATORY, THORACIC AND MEDIASTINAL DISORDERS** - Bronchopulmonary hemorrhage; Epistaxis; Hiccups; Hypoxia; Nasal congestion; Pleural effusion; Pleuritic pain; Pneumothorax; Postnasal drip; Productive cough

**SKIN AND SUBCUTANEOUS TISSUE DISORDERS** - Alopecia; Dry skin; Hyperhidrosis; Rash acneiform; Urticaria

**VASCULAR DISORDERS** - Flushing; Hypertension; Hypotension; Thromboembolic event

**Note:** MLN0128 (TAK-228) in combination with other agents could cause an exacerbation of any adverse event currently known to be caused by the other agent, or the combination may result in events never previously associated with either agent.

